#### **8.2.9.4. Dose Modification and Management of Toxicities**

Guidelines for dose modification are listed below.

**Table 10: Guidelines for Dose Modifications of CC-122 Related Toxicities**

Toxicity	Modification
Hematologic toxicities	
Grade 2 thrombocytopenia	
 
• No action
 

Grade 3 thrombocytopenia	
 
• Hold dosing until resolution to Grade <math>\leq 1</math> or baseline
 
• Follow complete blood count (CBC) at least every 7 days
 
• If resolution to Grade <math>\leq 1</math> or baseline occurs in <math>\leq 8</math> days, reintroduce CC-122 at the same dose level
 
• If AE resolution occurs after <math>> 8</math> days, or event reoccurs within the same cycle, reintroduce CC-122 at a lower dose level, if available
 

Grade 4 thrombocytopenia	
 
• Hold dosing until recovery to Grade <math>\leq 1</math> or baseline
 
• Repeat CBC within 24 to 48 hours
 
• Follow CBC at least every 7 days
 
• Reintroduce CC-122 at a lower dose level, if available
 

Grade 3 neutropenia	
 
• Hold dosing until resolution to Grade <math>\leq 1</math>
 
• Follow CBC at least every 7 days
 
• If AE resolution to Grade <math>\leq 1</math> occurs in <math>\leq 8</math> days, reintroduce CC-122 at the same dose level
 
• If AE resolution occurs after <math>> 8</math> days, or event reoccurs within the same cycle, reintroduce CC-122 at one dose level lower, if available
 

Grade 4 neutropenia	
 
• Hold dosing until recovery to Grade <math>\leq 1</math>
 
• Follow CBC at least every 5 days
 
• Reintroduce CC-122 at a lower dose level, if available
 
• Use of growth factors (granulocyte-colony stimulating factor [G-CSF], granulocyte macrophage-colony stimulating factor [GM-CSF]) is permitted at the discretion of the investigator
 

Febrile neutropenia	
 
• Hold further dosing until recovery to Grade <math>\leq 1</math> then resume dosing at one dose level lower, if available
 
• Use of growth factors (G-CSF, GM-CSF) is permitted at the discretion of the investigator
 

Any hematological toxicity requiring interruption for $> 4$ weeks	
 
• Discontinue CC-122
 

Non-hematologic toxicities	
Any Grade 4 non-hematologic toxicity, including LFT elevations	
 
• Hold dosing until recovery to Grade <math>\leq 1</math> (or baseline LFT if liver tumors are present)
 
• Reintroduce CC-122 at a lower dose level, if available
 

**Table 10: Guidelines for Dose Modifications of CC-122 Related Toxicities (Continued)**

Toxicity	Modification
Grade 3 or 4 clinical liver failure	
 
Discontinue CC-122
 

Troponin-T > ULN with associated 20% increase in BNP over baseline with an absolute value > 100 pg/mL (confirmed on repeated measurements) without associated cardiac symptoms or findings	
 
Hold dosing
 
Perform a cardiology evaluation, notify the sponsor
 
Follow troponin-T, BNP, and ECG at least every 7 days
 
If troponin-T returns to normal levels in <math>\leq</math> 7 days and there are no other significant cardiac findings, restart CC-122 at the next lower dose level or the same dose
 
If troponin-T elevation persists beyond 7 days or recurs upon rechallenge, permanently discontinue CC-122
 

Troponin-T > ULN with cardiac symptoms or significant changes in ECG or LVEF	
 
Permanently discontinue CC-122, notify the sponsor
 

Rash $\geq$ Grade 3	
 
If Grade 3, hold dosing until recovery to Grade <math>\leq</math> 1.
 
If AE resolution to Grade <math>\leq</math> 1 occurs in <math>\leq</math> 8 days, reintroduce CC-122 at the same dose level
 
If AE resolution to Grade <math>\leq</math> 2 or resolution after <math>></math> 8 days, reintroduce CC-122 at the next lower dose level, if available
 
Discontinue CC-122 for 2nd occurrence of <math>\geq</math> Grade 3 rash
 
For desquamating (blistering) Grade 3 or any Grade 4 rash, discontinue CC-122
 
For maculopapular, acneiform, or pustular rashes lasting <math>\leq</math> 7 days medical management is warranted
 

Pneumonitis $\geq$ Grade 3	
 
Discontinue CC-122
 

Grade 1 or 2 Tumor Flare Reaction (TFR)* * assessed according to NCI CTCAE Version 3.0	
 
Continue CC-122, maintain dose level
 
Nonsteroidal antiinflammatory drugs (NSAIDs) and/or narcotics may also be used as per the investigator's discretion
 
Initiate therapy with corticosteroids as per the investigator's discretion
 

Grade 3 or 4 TFR*	
 
Hold CC-122 dosing
 
Initiate therapy with corticosteroids
 
NSAIDs and/or narcotics may also be used as per the investigator's discretion
 
When symptoms resolve to <math><</math> Grade 1, restart CC-122 at the same dose level
 

**Table 10: Guidelines for Dose Modifications of CC-122 Related Toxicities (Continued)**

Toxicity	Modification
Peripheral neuropathy (neuropathies which begin or worsen while on study) $\geq$ Grade 3	
 
Hold dosing at investigator's discretion
 
When the toxicity resolves to <math>\leq</math> Grade 2 or to baseline, restart CC-122 at the next lower dose level
 

Allergic reaction or hypersensitivity $\geq$ Grade 3	
 
Discontinue CC-122
 

Venous thrombosis/embolism $\geq$ Grade 3	
 
Hold dosing and start anticoagulation therapy; restart CC-122 at the investigator's discretion (maintain dose level)
 

Other $\geq$ Grade 3 non-hematologic toxicity	
 
Hold dosing at the investigator's discretion
 
When the toxicity resolves to <math>\leq</math> Grade 2, restart CC-122 at the same dose level or at the next lower dose level at the investigator's discretion
 

Any non-hematologic toxicity requiring interruption for $> 4$ weeks	
 
Discontinue CC-122
 

Recurrence of Grade 3 non-hematologic toxicity after dose reduction	
 
Reduce dose to the next lower dose level, if available. If a lower dose is not available, discontinue CC-122
 

Recurrence of Grade 4 non-hematologic toxicity after dose reduction	
 
Discontinue CC-122
 

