**Table 8: DLT Criteria**

Toxicity	
Non-hematologic AEs	A clinically relevant non-hematologic AE that is suspected to be related to CC-122 and that commences during the DLT evaluation period and is $\geq$ Grade 3 EXCEPT for: 
 
Grade 3 rash of the acneiform or maculopapular type lasting <math>\leq</math> 4 days (with optimal medical management)
 
Grade 3 diarrhea or vomiting lasting less than 72 hours (with optimal medical management)
 

Laboratory abnormalities	A clinically relevant laboratory abnormality that is suspected to be related to CC-122 and that commences during the DLT evaluation period and is $\geq$ Grade 3
Hematologic	Any febrile neutropenia
	Grade 4 neutropenia lasting $>$ 7 days
	Grade 4 thrombocytopenia lasting $>$ 24 hours or thrombocytopenia of any grade requiring platelet transfusions
	Any Grade 3/4 thrombocytopenia with clinically significant bleeding
Hepatic	Grade 4 liver function tests (LFTs) or Grade 3 ALT with Grade 2 or higher bilirubin will be considered a DLT, irrespective of underlying attribution  However, other Grade 3 LFTs due to disease progression in the liver will not be considered DLTs
Other adverse events	Any adverse event suspected to be related to CC-122 and necessitating a dose reduction during the DLT evaluation period

Toxicities will be considered treatment-related unless clearly attributed to an alternative etiology (for example, tumor progression) by the investigator. Toxicities must be clearly not related to disease progression, medical procedures or intercurrent illnesses in order to be considered dose-limiting.

Isolated laboratory changes without associated clinical signs or symptoms will not be included in this definition. These findings will be discussed and reviewed by the SRC.

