### **8.2.9. Permitted Dosing Adjustments**

No dose reduction is allowed during the DLT evaluation period, except for subjects who experience DLTs. Subjects who experience DLTs during the DLT evaluation period will be allowed to resume CC-122 at a reduced dose once their toxicity recovers to Grade 1 or baseline, provided recovery occurs within 28 days of interrupting dosing. Dose reductions for non-dose-limiting toxicities are allowed after the DLT evaluation period after consultation with the sponsor.

Those continuing to take CC-122 beyond Cycle 1 may, following approval by the SRC, have their dose level increased, provided that the alternative dose level has been shown to be well-tolerated in at least one cohort of other subjects in this study. In these instances, additional PK evaluations at the higher dose level will be collected.

If a dose reduction is indicated, the next lower dose level will be selected. Two dose reductions are allowed, with the exception of the starting dose for which only one dose reduction is allowed. If any subject continues to experience unacceptable toxicity after 2 dose reductions, CC-122 will be discontinued permanently.

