#### **8.2.9.4.2. Dose Modification and Management of Pneumonitis**

Pneumonitis has been reported with CC-122. The diagnosis should be considered in subjects presenting with nonspecific respiratory signs and symptoms such as hypoxia, pleural effusion, cough, dyspnea, or interstitial pulmonary infiltrates, and in whom infectious, neoplastic and other causes are excluded by appropriate investigations. Subjects should be specifically advised to promptly report any new or worsening respiratory symptoms they experience.

CC-122 dosing for those with radiological features suggestive of noninfectious pneumonitis but with minimal (Grade 1) symptoms may be interrupted per the investigator's discretion. For drug-related Grade 2 pneumonitis, CC-122 treatment should be interrupted and corticosteroids may be indicated. Once symptoms have resolved completely, CC-122 may be reintroduced at the next lower dose level. For drug-related Grade 3 or 4 pneumonitis, CC-122 must be permanently discontinued and corticosteroids used until clinical symptoms have resolved.

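### Table 10 gives two incompatible instructions for a second non-blistering Grade 3 rash in a subject already dose-reduced with a lower level still available: the rash row stops CC-122, the Grade 3 recurrence row reduces and continues

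*Combined protocol and SAP*

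**What the plan says.** Three parts of the protocol bear on this.

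- **Table 10, rash row.** A first Grade 3 rash is held. If it settles to Grade 1 or lower within 8 days, dosing restarts at the same level. For slower or incomplete resolution the instruction ends "8 days, reintroduce CC-122 at the next lower dose level, if available". The row then says "Discontinue CC-122 for 2nd occurrence of" rash of Grade 3 or higher, with no condition on earlier reductions. Blistering Grade 3 rash and any Grade 4 rash stop treatment at any occurrence.
- **Table 10, Grade 3 recurrence row.** The trigger is "Recurrence of Grade 3 non-hematologic toxicity after dose reduction". The action is "Reduce dose to the next lower dose level, if available. If a lower dose is not available, discontinue CC-122". The row does not exclude rash and is not limited to toxicities without a row of their own.
- **Limits on reduction.** Section 8.2.9 allows two reductions, or one from the 2.0 mg starting dose. Section 8.2.9.1 sends the subject to the next lowest level tolerated by at least 3/3 or 5/6 subjects. Table 9 gives example steps by current dose.

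**The concern.** Rash is a non-hematologic toxicity in this protocol. Table 8 lists it among the non-hematologic events, and Table 10 places it under the non-hematologic heading. A repeat Grade 3 rash after a reduction therefore falls under both rows, and their actions cannot both be carried out.

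What is at stake is the handling of individual patients. A site that follows the recurrence row literally would re-expose, at a lower dose, a subject whom the rash row permanently stops. Two sites could also treat the same event differently while each followed the table.

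**Working it through.** No statistical figure is involved. The check applies both rows to the same event and looks for a rule that ranks them.

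**1. Can a subject reach the overlap?** Yes, by at least two routes.
- The rash row's own slow-resolution step: a subject on 4.0 mg has a non-blistering Grade 3 rash that takes more than 8 days to resolve and restarts at 3.0 mg.
- A Cycle 1 DLT: Table 8 exempts only "Grade 3 rash of the acneiform or maculopapular type lasting" 4 days or less under optimal management. A longer, clinically relevant, drug-related Grade 3 rash is a DLT, and under Section 8.2.9 the subject "will be allowed to resume CC-122 at a reduced dose once their toxicity recovers to Grade 1 or baseline", provided recovery comes within 28 days.

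**2. What does each row say at a second non-blistering Grade 3 rash?** The states are the post-reduction steps of Table 9.

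| Dose before reduction → dose now | Rash row | Recurrence row | Result |
|---|---|---|---|
| 2.0 → 1.0 mg | stop | no lower level: stop | agree |
| 3.0 → 2.0 mg | stop | 1.0 mg if it counts as available, otherwise stop | conditional |
| 3.0 → 2.0 → 1.0 mg | stop | two reductions used: stop | agree |
| 4.0 → 3.0 mg | stop | reduce to 2.0 mg | **conflict** |
| 4.0 → 3.0 → 2.0 mg | stop | two reductions used: stop | agree |

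**3. Is 2.0 mg available in the conflict row?** Yes. Under Section 8.2.7 escalation to 4.0 mg requires that the lower levels were cleared, with no DLT in at least 3 subjects or fewer than two among 6. That corresponds to the 3/3 or 5/6 standard of Section 8.2.9.1. The justification for Amendment 03 also records safety as confirmed at 2, 3 and 4 mg with the active-ingredient-in-capsule product. The move to 2.0 mg would be the second of two permitted reductions.

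**4. Who can be in that state?** Subjects who started at 4.0 mg, and also subjects who started lower. Sections 8.2.9 and 8.2.9.2 let the SRC approve escalation after Cycle 1 to a level shown to be well tolerated. Table 9 is keyed to current dose, so an escalated subject uses the 4.0 mg column.

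**5. The conditional row.** Table 2 uses 1.0 mg only if 2.0 mg is not tolerable, so it may never meet the 3/3 or 5/6 standard, although Table 9 shows it as a step. For the formulated capsules, lower doses are evaluated only as necessary.

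**6. Is precedence stated?** The introduction to Table 10 gives no ranking of rows. Neither do Sections 8.2.9, 8.2.9.1 or 8.2.9.3. The three subsections after the table cover cardiac laboratory abnormalities, pneumonitis and tumor flare; none covers rash.

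**The case against.** The strongest reply is that a specific row governs over a general one, so there is no true conflict. Much supports it. The rash row runs in sequence from restart, to restart at a lower level, to stopping at the second event, so its stop plainly contemplates a subject whom it has just reduced. Elsewhere the table works only on this principle. The row for "Any Grade 4 non-hematologic toxicity, including LFT elevations" allows re-introduction at a lower level, yet the rash row stops any Grade 4 rash. The troponin-T row carries its own recurrence rule, which Section 8.2.9.4.1 confirms. Read literally, the recurrence row would also collide with the tumor flare and venous thrombosis rows, which keep the dose level.

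This establishes the rash row as the natural reading. It does not supply a stated rule, and the table is not uniform. The neighboring row that discontinues after an interruption of more than 4 weeks for any non-hematologic toxicity has to apply to rash as well, since Section 8.2.9.3 caps delay at 4 weeks. So some closing rows do cut across the named ones. The drafters also limited one row to other toxicities, but not the recurrence row.

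The pneumonitis text adds little either way. Grade 3 pneumonitis stops treatment at first occurrence, so recurrence after reduction does not arise.

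Two safeguards also stand. The most severe rashes stop at any occurrence, and Section 8.2.9 requires sponsor consultation before a post-Cycle 1 reduction for a non-dose-limiting toxicity. Consultation lowers the risk, but the sponsor would still be consulting a table with two answers.

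**Conclusion.** Wrong as written, and minor. The conflict is definite for a subject reduced once from 4.0 to 3.0 mg who has a second, non-blistering, drug-related Grade 3 rash. It is conditional for a subject reduced from 3.0 to 2.0 mg, depending on whether a lower level counts as available. In the other steps of Table 9 both rows stop treatment.

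Three stronger readings are tempting and are not supported.

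- **That dose-finding is compromised.** In Cycle 1 a reduction is allowed only after a DLT, so a reduced subject has already been counted, and Section 8.2.7 counts subjects rather than events. After Cycle 1 no DLT is scored. DLT counts, the MTD rule and the planned analyses are unaffected.
- **That only 4.0 mg starters are exposed, or that the size of that cohort gives the share affected.** Intra-subject escalation can bring others to 4.0 mg, and Section 4.1.1 requires at least 6 subjects at the MTD/RP2D, so that cohort may grow. A cohort share is in any case not a risk, and the documents give no rate of repeat Grade 3 rash. No percentage should be quoted.
- **That the plan intends to re-expose these subjects.** The rash row points the other way and is the safer and more natural instruction.

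**What to change.** Add to the Grade 3 recurrence row of Table 10: *except where a toxicity-specific row above requires discontinuation (e.g., second occurrence of Grade 3 or higher rash)*.

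This keeps the evident intent of the rash row and leaves the recurrence row in force for toxicities without their own stopping rule. It costs one clause in one row and can go into the next amendment. It adds no procedures, visits or subjects and changes no analysis.

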#### 8.2.9.4.1. Dose Modification and Management of Cardiac Laboratory Abnormalities

In addition to routine ECG monitoring, additional monitoring for potential cardiac toxicity is included for subjects treated with CC-122. This includes routine monitoring of troponin-T and BNP, as well as monitoring of LVEF as described in Section 6. Elevations of troponin-T or BNP warrant further investigation, including assessment of the subject for signs and symptoms of cardiac injury, consideration of a cardiology consultation, other cardiac evaluations (such as an exercise stress test, additional evaluation of LVEF, or other cardiac tests recommended by a cardiologist), and the addition of cardioprotective therapy (for example, beta blockers), as appropriate. Laboratory evaluation to assess for assay interference may also be warranted.

Isolated asymptomatic elevations of troponin-T or BNP without associated ECG or LVEF changes or other cardiac findings do not require that dosing be held. For any elevation of troponin-T  $>$  ULN associated with either significant elevation of BNP (20% increase from baseline with an absolute value  $>$  100 pg/mL) or associated cardiac symptoms or findings, CC-122 dosing should be held and the sponsor should be notified. Additional cardiac monitoring should be performed as described in the table above and as medically indicated. CC-122 may be restarted, in consultation with the sponsor, based on troponin-T/BNP guidelines in Table 10 and general guidelines provided in Sections 8.2.9.1 and 8.2.9.3. For troponin-T elevations that either persist, recur with CC-122 rechallenge and/or are associated with cardiac symptoms or significant changes in ECG or LVEF, CC-122 should be permanently discontinued.

#### **8.2.9.4.2. Dose Modification and Management of Pneumonitis**

Pneumonitis has been reported with CC-122. The diagnosis should be considered in subjects presenting with nonspecific respiratory signs and symptoms such as hypoxia, pleural effusion, cough, dyspnea, or interstitial pulmonary infiltrates, and in whom infectious, neoplastic and other causes are excluded by appropriate investigations. Subjects should be specifically advised to promptly report any new or worsening respiratory symptoms they experience.

CC-122 dosing for those with radiological features suggestive of noninfectious pneumonitis but with minimal (Grade 1) symptoms may be interrupted per the investigator's discretion. For drug-related Grade 2 pneumonitis, CC-122 treatment should be interrupted and corticosteroids may be indicated. Once symptoms have resolved completely, CC-122 may be reintroduced at the next lower dose level. For drug-related Grade 3 or 4 pneumonitis, CC-122 must be permanently discontinued and corticosteroids used until clinical symptoms have resolved.

#### **8.2.9.4.3. Dose Modification and Management of Tumor Flare Reaction**

Subjects in this study should be monitored for tumor flare. Tumor flare reaction (TFR) is defined as a sudden and tender increase in the size of the disease bearing sites, including the lymph nodes, spleen and/or the liver often accompanied by low-grade fever, nonpruritic diffuse rash and in some cases increase in the peripheral blood lymphocyte counts. Tumor flare usually occurs within the first cycle of treatment. Tumor flare reaction may mimic progression of disease (PD); however, the TFR will generally subside over time. Therefore, careful monitoring and evaluation is important prior to discontinuing a study subject for PD in the initial cycles of CC-122 therapy.

There are currently no laboratory or radiological tests that distinguish TFR from PD. The distinction should be made on clinical grounds, incorporating observations such as associated physical findings, laboratory findings, and pace of disease before and after institution of treatment. Tumor flare will be recorded as an AE (graded using the NCI CTCAE 3.0 criteria) and not as PD.

Treatment of the TFR is up to the discretion of the investigator, depending on the severity and clinical situation. Recommendations for treatment are outlined in [Table 10](#). Refer to [Table 10](#) for further instructions and dose modifications for Grades 3 and 4 TFR. In mild to moderate cases, it is suggested that CC-122 be continued along with symptomatic treatment as outlined above. In more severe cases, CC-122 should be interrupted, as indicated in [Table 10](#).

#### **8.2.9.5. Overdose**

An overdose, as defined for this protocol, refers to CC-122 dosing only.

On a per dose basis, an overdose is defined as the following amount over the protocol-specified dose of CC-122 assigned to a given subject, regardless of any associated adverse events or sequelae.

- PO any amount over the protocol-specified dose

On a schedule or frequency basis, an overdose is defined as anything more frequent than the protocol required schedule or frequency.

Complete data about drug administration, including any overdose, regardless of whether the overdose was accidental or intentional, should be reported in the case report form. See Section [11.1](#) for the reporting of adverse events associated with overdose.

In the event of overdose, the subject should be monitored as appropriate and should receive supportive measures as necessary. There is no known specific antidote for CC-122 overdose. Actual treatment should depend on the severity of the clinical situation and the judgment and experience of the treating physician.

### **8.3. Method of Treatment Assignment**

All subjects enrolled on this study will receive treatment with CC-122.

The investigators must explain the study to prospective patients, using the informed consent form and obtain the written consent from patients who wish to participate in the study prior to screening assessments. After the confirmation of the inclusion and exclusion criteria, the investigators will fax an enrollment form (if subject is eligible) to the registration center. After receiving confirmation from the registration center, dosing should be started within 7 days of receiving the confirmation of registration.

As this is a dose-escalation trial, the assignment of a subject to a particular dose level will be coordinated by the sponsor and the investigator.

